TITLE PAGE

New Therapeutical Perspectives in Cases of Phonological
Disorders

28053914.1.0000.5346

DOCUMENT DATE: 20/11/2018

STUDY PROTOCOL WITH SAP- STATISTICAL ANALYSIS PLAN

Objectives: The objective of this research was to analyze and compare phonological aspects such as phonetic inventory, phonological system, severity of the speech sound disorders, altered distinctive traits and phonological processes, as well as phonological and phonoarticulatory awareness, besides the auditory aspects of the abilities and variables present in Long Auditory Evoked Potential Long. Comparisons of the phonological and auditory aspects were performed before and after the intensive period of treatment in children with speech sound disorders. Twenty-five therapy sessions were assigned. The children were randomly drawn among three groups. Group 1 - Placebo: This group received no specific treatment for speech deviations, only used the computer resource to play on a website. The Group 2-Cycles Traditional: the therapy used the Modified Cycles Model. And the Group 3-SIFALA ("Speech Intervention Software"): the therapy used the proposal of the Strata Model based on Stimulability and Segment Complexity that was developed in software format. The categorization of these groups obeys the methodological questions of a randomized clinical trial. The evaluation of the children and the treatment of one of the SIFALA group were carried out by the responsible researcher. The other two groups were treated by fellowship academics of the Speech Language Pathology program. The reassessment of all procedures was performed by speech language pathologists with experience in speech and hearing areas who did not have knowledge about the variables of the research, so it was categorized as a single-blind trial. After the treatment period, the data were compared by means of the statistical analysis that used as a criterion to estimate the effects in each therapy group using the linear regression model with mixed effects for the quantitative variables responses. Also

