was used the polytomous logistic model for ordinal qualitative variables. In addition, Chi-Square and Wilcoxon tests were used for analysis of the abilities and variables of Long Auditory Evoked Potential. A significance level of 0.05 was set for all tests. Most of the children treated presented gains in the phonological and auditory variables. The therapeutic models used fulfilled the objective of reorganization of the phonological system, being possible to point out as innovative and differentiated the model using *software*-SIFALA. Key Words: Children. Language. Speech Sound Disorders. Auditory Perception. Rehabilitation of Speech Sound Disorders.

STATISTICAL ANALYSIS PLAN

The variables chosen for the static analyzes characterize the phonological and auditory aspects of the evaluations applied before and after the treatment period. For the phonological aspects, we adopted the variables that determine the phonological system, dividing sounds by the following criteria: acquired, partially acquired and not acquired; (SHRIBERG et al., 1997), altered distinctive traits and phonological processes. The PCFO (SEABRA and CAPOVILLA, 2012) and the evaluation of phonoarticulator awareness – CONFIART (SANTOS, VIEIRA and VIDOR-SOUZA, 2014) were also analyzed. For the auditory aspects of the LAEP, the variables were the measures of latency and amplitude of the right and left ears, as well as the qualitative description of the occurrence of the P300 wave. The main statistical method used as a criterion for estimating the effects in each therapy group was the linear regression model with mixed effects (FAUSTO et al., 2008; PINHEIRO et al., 2017) for the quantitative response variables. This model uses fixed effect for the therapy group and random effects for children in the treatment periods, extracting information from the data more accurately than the traditional linear models, which usually use only fixed effects for the explanatory

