variables. The main inferential utility of the linear regression model is related to the interpretation of the significant coefficients, with which it is possible to have an estimate for the change in the level of the phonological aspects considered in the research, among them: phonetic inventory, phonological system, distinctive features and phonological processes. The polytomic logistic model was also used for the variables of ordinal qualitative responses, which included the analysis of PCFO performance (SEABRA and CAPOVILLA, 2012) and the evaluation of phonoarticulatory awareness. (SANTOS, VIEIRA and VIDOR-SOUZA, 2014). The advantage of the application of logistic models is mainly the determination of the odds factor through the exponentiation of the estimated coefficients. Other tests involved in validating the results include Fisher's Exact, ShaphiroWilk and Levene T for correlated samples and Analysis of Variance. Chi-Square and Wilcoxon tests were applied to the PEALL variables. For all hypothesis tests, a significance level of 0.05 was set.

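### The tests expressly assigned to the LAEP outcomes, Chi-Square and Wilcoxon, give no three-arm comparison of before/after change in latency and amplitude, and no other stated analysis clearly supplies one

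*Combined protocol and SAP*

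**What the plan says.** The Objectives section sets a randomised comparison of placebo, Modified Cycles and SIFALA: "The children were randomly drawn among three groups". Auditory aspects are within its scope: "Comparisons of the phonological and auditory aspects were performed before and after the intensive period of treatment".

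The Statistical Analysis Plan defines the LAEP (long auditory evoked potential) variables as "the measures of latency and amplitude of the right and left ears, as well as the qualitative description of the occurrence" of the P300 wave. That makes two quantitative measures per ear and one categorical outcome.

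Tests are tied to these variables in two places. The Objectives summary says: "In addition, Chi-Square and Wilcoxon tests were used for analysis of the abilities and variables of Long Auditory Evoked Potential". The closing lines of the Statistical Analysis Plan say: "Chi-Square and Wilcoxon tests were applied to the PEALL variables". I take PEALL and LAEP to be the same set of variables, since the same pair of tests is named for both.

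The main method is a linear mixed model "for the quantitative response variables. This model uses fixed effect for the therapy group and random effects for children in the treatment periods". The plan later describes its coefficients as estimating change in phonological aspects, and the examples given include no auditory measure. Fisher's Exact test and Analysis of Variance are listed among tests for validating results, with no outcome attached. Every test uses a 0.05 level.

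The summary concludes: "Most of the children treated presented gains in the phonological and auditory variables".

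**The concern.** A placebo arm allows a therapy effect to be told apart from gains that any child might show over the same period, through maturation or familiarity with the test. Those gains would appear in all three arms. Only a between-arm contrast of the before/after change removes them.

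The tests named for LAEP do not clearly deliver that contrast for latency and amplitude. If Wilcoxon means signed-rank, each arm is compared with itself, and the reader is left to compare one p-value with another. If it means rank-sum, arms are compared in pairs, with no statement of which pairs, whether change is the quantity compared, or how the 0.05 level is shared. Chi-Square does not apply to a continuous measure unless it is categorised, and no categories are given. At stake is the auditory half of the trial's conclusion, which is worded as gains among treated children and not as a difference from placebo.

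**Working it through.** The plan gives no sample size, SD, effect size or power, so there is no figure of its own to reproduce. The main check is to match each method to the data: three arms, two visits, a continuous outcome.

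**Methods against data**

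| Method in the plan | What it compares | Between-arm contrast of change in latency or amplitude? |
|---|---|---|
| Wilcoxon signed-rank | Before with after, one arm | No |
| Wilcoxon rank-sum | Two arms | Pairwise only, if applied to change; no multiplicity rule |
| Chi-Square | Categories | No; suitable for P300 occurrence |
| Mixed model, if it covers LAEP | Therapy group named as fixed effect | Not stated: no period or group-by-period term |
| Analysis of Variance | No outcome named | Not stated |

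The remaining steps are illustrations. Assumed, not from the documents: 8 to 20 children per arm, normally distributed change, two-sided 0.05. SD means the SD of a child's before/after change.

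**1. Separate signed-rank tests, equal true change in every arm.** Let q be the probability that one arm is not significant. The misleading pattern is that placebo is not significant and at least one of the two active arms is:

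P = q × (1 − q²)

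This is largest where 1 − 3q² = 0, so q = 0.577 and P = 0.577 × (1 − 0.333) = 0.385. The pattern therefore cannot exceed about 38.5%, apart from simulation error. Results from 10,000 simulated trials per setting:

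| Children per arm | 8 | 10 | 12 | 15 | 20 |
|---|---|---|---|---|---|
| Change 0.5 SD | 0.285 | 0.344 | 0.356 | 0.385 | 0.357 |

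The range over these arm sizes is 0.158-0.325 at 0.3 SD and 0.089-0.380 at 0.8 SD.

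**2. Three pairwise rank-sum tests on change, no true difference.** At least one p < 0.05 in 0.105-0.131 of trials. Three independent tests would give 1 − 0.95³ = 0.143; these share arms, so the rate is lower. One three-arm rank test (Kruskal-Wallis) on change gives 0.044-0.052.

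**3. Power of the contrast of change.** One arm changes 0.8 SD more than the other two. The arm means are 0.8, 0 and 0, with mean 0.267, so their sum of squares about the mean is 0.64 − 3 × 0.267² = 0.427 = 0.64 × 2/3. The noncentrality is λ = n × 0.64 × 2/3, with 2 and 3n − 3 degrees of freedom.

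| n per arm | λ | Power |
|---|---|---|
| 8 | 3.41 | 0.318 |
| 12 | 5.12 | 0.476 |
| 20 | 8.53 | 0.723 |

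**4. One hypothetical mixed-model fit.** Suppose group were the sole fixed effect, with a random child effect. In balanced data the group coefficient then compares child means over both visits. A 0.80 SD difference present only after treatment is estimated as (0 + 0.80)/2 = 0.40 SD. With before/after correlation assumed at 0.3 to 0.7 and n from 8 to 20, power is 0.093-0.448, against 0.314-0.728 for the contrast of change in the same simulated trials. The plan does not say that group is the sole fixed effect, so this shows only what leaving the period terms open could cost.

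**The case against.** The strongest reply is that the mixed model already covers latency and amplitude. It is the main method for quantitative responses, the sentence follows directly after those measures are listed, and the Wilcoxon and Chi-Square tests are introduced as additions. This reading is arguable, although the plan's account of the model's change estimates mentions phonological aspects only. It does not close the gap, because no period or group-by-period term, and no contrast of change, is stated.

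A second reply is that separating therapy from maturation needs a comparison with placebo, not an omnibus three-arm test, and rank-sum on change for each active arm against placebo would supply it. That is correct. What would then remain is multiplicity, a smaller matter, and the fact that the plan does not say rank-sum, change scores or placebo.

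Third, the numbers are conditional. This stands: no sample size, SD or effect size is in the documents, and the signed-rank figure applies only if arms are read from separate tests, which the plan does not say.

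Several stronger readings are tempting, and the documents do not support them:

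- That 28%-38% is the plan's type I error. It is the frequency of one pattern under one way of reading the results.
- That the plan fits group as the only fixed effect and loses half the treatment effect. The text names group; it does not exclude other terms.
- That Chi-Square is wrong for P300 occurrence. Across arms it is a valid comparison; the plan only omits to say that arms are what it compares.
- That the two ears were pooled as independent. Their handling is not described.
- That the summary claims superiority over placebo on auditory measures. It reports gains, for phonological and auditory variables together.

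**Conclusion.** The concern holds for latency and amplitude. Chi-Square and Wilcoxon are the only tests expressly assigned to them, and neither is a three-arm comparison of change. The mixed-model reading leaves the needed term unstated. On the analyses as written, auditory gains within arms cannot be separated from maturation or retest.

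This conclusion rests on the text and not on the simulations. With 8-20 per arm assumed, the misleading signed-rank pattern occurs in about 28%-38% of trials at an equal 0.5 SD change, and in 9%-38% across 0.3-0.8 SD, if arms are judged from separate tests. Unadjusted pairwise rank-sum tests give about 11%-13% false positives, against 4%-5% for a single three-arm test. The point should be acted on, but it is repairable: the plan already contains a suitable model and does not name LAEP as primary.

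**What to change.** - **Latency and amplitude:** use the plan's mixed model with group, period and group-by-period as fixed effects, child as a random effect, and ear as a within-child factor (or analyse the mean of both ears). Base the auditory conclusion on the between-arm contrast of change.
- **Wilcoxon:** say which form is meant, and keep signed-rank as a description of change within each arm.
- **P300 occurrence:** keep Chi-Square, or the already listed Fisher's Exact if counts are small, and state that it compares the three arms.
- **Status:** the document is written in the past tense and reports results. If the LAEP results are already known, label the re-analysis post hoc.

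The cost is a few lines of SAP wording and a re-analysis of existing data; no new data are needed. The downside is modest power: for one arm changing 0.8 SD more than the other two, about 32% at 8 per arm, 48% at 12 and 72% at 20. A non-significant contrast should therefore not be reported as evidence of no auditory effect.

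### Every test is run at 0.05 with no primary outcome, testing order or multiplicity control, so the chance of at least one false positive is at least twice nominal in every scenario examined

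*Combined protocol and SAP*

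**What the plan says.** The error rule appears twice. The Objectives section has "A significance level of 0.05 was set for all tests", and the Statistical Analysis Plan repeats it: "For all hypothesis tests, a significance level of 0.05 was set".

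The plan calls a method main, but never an outcome: "The main statistical method used as a criterion for estimating the effects in each therapy group" is the mixed-effects linear model. It describes the model's chief inferential use as the "interpretation of the significant coefficients, with which it is possible to have an estimate for the change in the level" of the phonological aspects, so significance decides which estimates are interpreted.

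The contrasts are not listed. Children are randomised to three groups and the model has a therapy-group effect, but no pair of groups is given priority. Before-after comparisons are also described: "Comparisons of the phonological and auditory aspects were performed before and after the intensive period of treatment". The supporting tests include "T for correlated samples and Analysis of Variance". For the auditory outcomes, "the variables were the measures of latency and amplitude of the right and left ears", plus P300 occurrence. The plan says only that "Chi-Square and Wilcoxon tests were applied to the PEALL variables", without stating whether these tests compare groups or time points.

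**The concern.** With one test, a 0.05 level limits the false-positive risk to 5%. With many outcomes and three arms, each tested at the full 0.05, the risk that something reaches significance by chance grows with the number of tests. No primary outcome or testing order says which result counts. A reader who meets one significant coefficient then cannot tell a therapy effect from the expected yield of many looks, and interpreting the significant coefficients also favours estimates that are large by chance.

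A separate problem affects the before-after tests. A change within one group does not separate therapy from change that would have occurred anyway, so such a test cannot support a therapy claim even when its error rate is controlled.

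The documents do not show that the favourable statement about the SIFALA software in the Objectives section rests on an isolated p-value, and this point does not claim that it does.

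**Working it through.** **Inputs from the documents.** Level 0.05 for each test; three arms, hence three possible pairs. No sample size, power or familywise error rate is given, so there is no figure of the plan's own to reproduce.

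**Outcome count (m), from the Objectives and the Statistical Analysis Plan.**

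- Phonetic inventory 1, phonological system 1, distinctive traits 1, phonological processes 1, PCFO 1, CONFIART 1
- Latency and amplitude for each ear: 2 × 2 = 4
- P300 occurrence 1
- Total: 6 + 4 + 1 = 11
- Adding severity (named in the objectives, not legible in the SAP list): 12
- Counting acquired, partially acquired and not acquired sounds separately: 12 + 2 = 14
- Without the five auditory outcomes: 11 − 5 = 6, or 14 − 5 = 9

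The auditory abilities mentioned in the Objectives are not enumerated and are not counted.

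**Assumptions.** All null hypotheses true; two-sided normal tests; equal arms; one common correlation between outcomes, from 0 to 0.9 because the documents give none. Correlation 0 is the least plausible case: the acquisition categories share sounds, and both ears belong to one child.

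**One between-arm contrast per outcome, independent outcomes.** The chance of at least one false positive is 1 − 0.95^m:

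- m = 14: 1 − 0.95^14 = 0.512
- m = 11: 1 − 0.95^11 = 0.431
- m = 9: 1 − 0.95^9 = 0.370
- m = 6: 1 − 0.95^6 = 0.265

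**Correlated outcomes and three pairs.** These come from simulation, which keeps the dependence between contrasts that share an arm. (Treating 14 × 3 = 42 tests as independent would overstate the rate at 1 − 0.95^42 = 0.884.)

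| Scenario | m | ρ = 0 | 0.3 | 0.5 | 0.7 | 0.9 |
|---|---|---|---|---|---|---|
| One contrast | 14 | 51% | 44% | 35% | 25% | 14% |
| One contrast | 11 | 43% | 38% | 30% | 22% | 13% |
| One contrast | 9 | 37% | 32% | 27% | 20% | 12% |
| One contrast | 6 | 26% | 24% | 21% | 16% | 11% |
| Three pairs | 14 | 84% | 76% | 65% | 50% | 31% |
| Three pairs | 11 | 76% | 69% | 59% | 46% | 29% |
| Three pairs | 9 | 69% | 63% | 54% | 42% | 27% |
| Three pairs | 6 | 54% | 50% | 44% | 35% | 25% |

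**Before-after tests.** Adding one per group and outcome to the three pairs, and assuming no true change over time, gives 44–94% for m = 14 and 41–90% for m = 11. If instead every arm changes by the same 2 standard errors (assumed), each before-after test is significant with probability Φ(2 − 1.96) + Φ(−2 − 1.96) = 0.52, with no difference between therapies.

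**The case against.** The strongest objections concern the size of the problem rather than its existence.

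- **Pairs may be gated.** The plan lists analysis of variance and fits a therapy-group effect, so a three-arm test at 0.05 could precede the pairs. Under that gate the rates are 51 / 36 / 15% (m = 14) and 43 / 31 / 14% (m = 11) at correlation 0 / 0.5 / 0.9, close to the one-contrast figures. The plan describes no gate, but it does not describe three ungated pairs either. The 29–84% range is therefore a scenario. Two contrasts, each therapy against placebo, give 25–74% (m = 14) and 23–65% (m = 11).
- **The count is soft.** A stricter reading gives 10 outcomes: about 13–40% with one contrast and 28–73% with three. Treating phonological and auditory outcomes as separate families of 6–9 and 5 gives about 11–37% and 10–23% with one contrast. Every one of these is still at least twice 5%.
- **The before-after figures are the weakest.** The paired t-test appears in a list of supporting tests, which does not establish one per group and outcome. Absence of any change over 25 sessions is also hard to assume. This stands: those figures are conditional and the conclusion does not need them.
- **Normal tests are a simplification.** Exact tests can run below 5% in small samples, and the sample size is not given. The percentages are approximate.
- **The document is in the past tense and reports results.** Prespecification cannot now be added. That shapes the fix but does not remove the problem. If the work was exploratory, the document does not say so.

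**Conclusion.** The concern holds. The stated rule gives every test the full 0.05 and nothing in the document offsets it. For 11 to 14 outcomes the familywise false-positive chance is about 13–51% with one between-arm contrast each, a range that also covers a gated three-arm test, and 29–84% with three ungated pairs. The lowest figure in any scenario examined is about 10%.

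The exact size depends on the outcome count, the contrasts actually made and the assumed correlation, none of which the documents settle. The direction does not depend on them. The point should be fixed before any single significant result is used to support a therapy.

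**What to change.** 1. List every outcome and every contrast tested, and state whether the auditory tests compare arms or time points.
2. Base therapy claims on the between-arm comparison of change. Label within-group before-after tests descriptive, with no significance claim.
3. If dated evidence shows that one outcome was designated before data review, test it at 0.05 (three-arm test, then pairs) and label the rest exploratory.
4. Otherwise label all results exploratory. Make a confirmatory claim only if it survives an adjustment over all m outcomes that carries through to the pairs: 0.05/m at both the three-arm and the pairwise step, or a resampling max-statistic over all m × 3 contrasts. Fix m from the outcomes measured, not those reported.
5. Report every estimate with its confidence interval, significant or not.

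In simulation (no effect, and placebo differing on all or half of the outcomes) familywise error was 0.014–0.050 with 0.05/m at both steps and 0.017–0.052 with the max-statistic.

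**Cost.** Wording, labels and adjusted p-values; no new data. The exploratory label costs no power. A confirmatory claim without a pre-designated outcome does. A contrast with 80% power at 0.05 has a z shift of 1.960 + 0.842 = 2.802. The critical values at 0.05/m are 2.91 (m = 14) and 2.84 (m = 11), so power is at most 46% and 49%. With the three-arm step it is about 40% and 43% if the third arm equals one of the pair, or 34% and 37% if it lies midway. The max-statistic gives about 34–50% (m = 14) and 36–51% (m = 11) across correlation 0 to 0.9; whether resampling is feasible depends on the sample size, which is not stated. Some nominally significant results would lose that status.
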